4.4. End of Study Definition

A participant is considered to have completed the study if he/she has completed all phases of the study including the last scheduled procedure shown in the Schedule of Activities (SoA). The end of the study is defined as the date the last participant completes the last visit shown in the SoA (Section 1.3).

5. STUDY POPULATION

Prospective approval of protocol deviations to recruitment and enrollment criteria, also known as protocol waivers or exemptions, is not permitted.

5.1. Inclusion Criteria

Age

1. Participants aged ≥ 18 at the time of signing the ICF.

Type of Participants and Disease Characteristics

2. Diagnosis of WD by Leipzig Criteria ≥ 4 documented by testing as outlined in the 2012 European Association for the Study of Liver WD Clinical Practice Guidelines ([Ferenci, 2003](#); [EASL, 2012](#)) or by historical test results for WD including some or all of the following:
 - Presence of Kayser Fleischer rings,
 - Neurological symptoms,
 - Serum ceruloplasmin below reference range,
 - Coombs-negative hemolytic anemia,
 - Elevated liver or urinary copper,
 - Presence of mutations in the ATP7B gene, or
 - Other, as considered appropriate, may be used instead to confirm the diagnosis of WD.
3. Participants who in the opinion of the referring Investigator may benefit from decoppering therapy.
4. Participants must be able to comply with all study-related procedures.
5. Participants must be able to reside in the CRU for intensive metabolic monitoring of copper and molybdenum.
6. Participants willing to discontinue chelator therapy for approximately 4 days prior to initiation of ALXN1840 to allow a baseline assessment of copper balance.
7. Participants with adequate venous access to allow collection of required blood samples.
8. Participants must be able to swallow intact ALXN1840 tablets.
9. Participants willing to avoid use of minerals containing copper, zinc, or molybdenum throughout the study duration.
10. Participants willing to adhere to copper/molybdenum-controlled diet during inpatient periods and willing to comply with a low copper dietary requirement during the Outpatient Period.

Sex

11. Contraceptive use by men or women should be consistent with local regulations regarding the methods of contraception for those participating in clinical studies.
 - a. Male participants:
 - Male participants, if heterosexually active and with a female spouse or partner of childbearing potential or a pregnant or breastfeeding spouse or partner, must agree to use barrier contraception (male condom) for the duration of the study and for at least 3 months after the end of systemic exposure of the study intervention. Male

- participants must not donate sperm for at least 3 months after the end of systemic exposure of the study intervention.
- Female spouses or partners of male participants who are of childbearing potential must use highly effective contraception as defined below and in Section 10.4, starting at least 1 menstrual cycle before (the male participant's) first study intervention administration and continuing until at least 3 months after the end of their male partner's systemic exposure to the study intervention.
 - Barrier contraception (male condom) is required even with documented medical assessment of surgical success of a vasectomy. For male participants who have had a vasectomy (with documented evidence of azoospermia if possible) and agree to use a male condom for the stated time period, no additional contraceptive method is required by their female partner.
- b. Female participants:
- Female participants or female partners of male participants of childbearing potential (including breastfeeding females), if heterosexually active, must be willing to follow protocol-specified contraception guidance starting at least 1 menstrual cycle before first study intervention administration and continuing for at least 3 months after the end of systemic exposure of the study intervention. Female participants must not donate ova for at least 3 months after the end of systemic exposure of the study intervention.
 - Female participants who are documented as being of non-childbearing potential as defined in Section 10.4 are exempt from contraception requirements.
 - Highly effective contraceptive methods for female participants and female partners of male participants are described in Section 10.4.

Informed Consent

12. Participants capable of giving signed informed consent, which includes compliance with the requirements and restrictions listed in the ICF and in this protocol.

5.2. Exclusion Criteria

Medical Conditions

1. Decompensated cirrhosis or model for end-stage liver disease (MELD) score > 13.
2. Modified Nazer score > 7 (Dhawan, 2005).
3. Clinically significant gastrointestinal bleed within past 3 months.
4. Alanine aminotransferase (ALT) > 2 × upper limit of normal (ULN).
5. Marked neurological disease requiring assistance with self-care or activities of daily life.
6. Hemoglobin less than lower limit of the reference range for age and sex.
7. Active infection with hepatitis B virus (positive hepatitis B surface antigen) or C virus (participants with positive hepatitis C antibody result would require confirmation of active disease with a positive hepatitis C polymerase chain reaction test), or seropositivity for human immunodeficiency virus (HIV).

8. History or presence of/significant history of or current cardiovascular, respiratory, hepatic, renal, gastrointestinal, endocrinological, hematological, or neurological disorders, or psychiatric disorder that in the opinion of the Investigator may constitute a risk when taking the study intervention; or may interfere with the interpretation of data.

Prior/Concomitant Therapy

9. Previous treatment with ALXN1840 or other form of tetrathiomolybdate within 1 year prior to dosing.
10. Previous treatment with zinc within 21 days prior to Day 1.

Prior/Concurrent Clinical Study Experience

11. The use of an experimental or unapproved/unlicensed therapy at the same time or within 90 days or 5 half-lives, whichever is longer, prior to the Screening Visit.

Diagnostic Assessments

12. Participants in renal failure, defined as in end-stage renal disease on dialysis (chronic kidney disease [CKD] stage 5) or creatinine clearance < 30 mL/min (Levey, 2006).

Other Exclusions

13. Pregnant (or females who are planning to become pregnant) or breastfeeding females (women of childbearing potential must have a negative serum pregnancy test result at screening).
14. Known sensitivity to ALXN1840, ALXN1840 excipients (anhydrous dicalcium phosphate, anhydrous sodium carbonate), or any of the ingredients contained in ALXN1840 or related compounds.
15. In the opinion of the Investigator, the participant and/or their legal guardian is likely to be non-compliant or uncooperative during the study.
16. History of illicit drug abuse, history of significant alcohol abuse within 1 year prior to the Screening Visit, or clinical evidence of substance and/or alcohol abuse within the 2 years before screening. Alcohol abuse is defined as regular weekly intake of more than 14 units (for both males and females), using the following National Health Service (NHS) alcohol tracker <http://www.nhs.uk/Tools/Pages/drinks-tracker.aspx>.
17. Positive urine drug toxicology screen at Screening or on Day -8 (cannabinoids will not be tested).
18. Alcohol consumption within 48 hours prior to study intervention administration or positive alcohol breath test at screening or on Day -8.
19. Participants unwilling to consistently complete every meal and tolerate a controlled, limited menu for the duration of the study.

5.3. Lifestyle Considerations

Participants must be able and willing to adhere to the lifestyle restrictions detailed in [Table 5](#).

Table 5: Participant Lifestyle Considerations

Restrictions	Timeframe Restriction Applies	Restrictions End

Food Participants will remain on a copper/molybdenum-controlled diet. Standardized copper- and molybdenum-controlled meals will be provided. Male participants will receive larger meals than female participants, with adequate meal size to ensure appropriate daily caloric intake. If a participant is unable to eat 100% of the food, the remaining food will be weighed and reported in the CRF to support copper/molybdenum determination as a fraction of the total meal. Participants will be expected to fast overnight. During the dosing period, participants will be administered ALXN1840 with 240 mL of water each morning; participants must remain fasted for a least 2 hours after dose administration.
	
Dietary restrictions will remain in place during Inpatient Periods 1 and 2.
	
Participants may return to routine diet after completion of Day 40.

Fluids All participants will drink water from the same large water bottle dispenser. There will be no set maximum volume of water that the participants must consume, but there will be a minimal volume that they must consume each day (1.5 L). The precise volume that each participant consumes will be measured.
	
Water restrictions will remain in place during Inpatient Periods 1 and 2.
	
Participants may return to routine fluid intake after completion of Day 40.

Alcohol
	
48 hours before check-in to the CRU (Day -8 and Day 22/23) and until discharge on Day 40, and 48 hours before each study Outpatient/Follow-up Visit.
	
Discharge from the CRU and completion of EOS Visit.

Physical activity Participants will carry out daily scheduled light exercise. This is to help encourage regular bowel movements and for health benefits to the participants. Participants must refrain from strenuous activity for 24 hours prior to each study visit for the duration of the study.
	
48 hours prior to check-in to the CRU (Day -8 and Day 22/23) and until discharge on Day 40.
	
Restrictions end after completion of EOS Visit.


Concomitant medication Concomitant medication guidelines are as per Section 6.5. Note: If participants have a medical need to take any new medication(s) prescribed to them by a doctor, they should follow the medical advice but inform the Investigator as soon as possible afterwards. Investigator in consultation with Alexion should determine participant’s continued suitability to remain in the study.
	
Signing of informed consent until EOS Visit.
	
Restrictions ends after completion of EOS Visit.

Restrictions	Timeframe Restriction Applies	Restrictions End

Nonprescription/over-the-counter medication Any nonprescription/over-the-counter medication may be taken under the direction of the Investigator. Over-the-counter medications may be given if they are not expected to impact the outcome of the study. Acetaminophen should be limited to 1000 mg/day. Herbal remedies must be discontinued at least 7 days prior to first admission until study completion.
	
Allowed under direction of Investigator.
	
After the EOS Visit.

St John's wort Any herbal remedy or dietary supplement containing St John's wort.
	
2 weeks before the planned first study intervention is administered.
	
After EOS Visit.

Blood and plasma donation
	
Blood donation or blood loss in excess of 500 mL in the 60 days prior to screening (Section 5.2).
	
1 month after EOS Visit.

Contraception Participants must consistently and correctly use one or more of the appropriate contraceptive methods described in Section 10.4.
	
Start times for contraceptives vary according to method used (see Section 5.1 [inclusion criteria]).
	
See Section 10.4.

Abbreviations: CRF = case report form; CRU = clinical research unit; EOS = End of Study; SoA = Schedule of Activities.

5.4. Screen Failures

Screen failures are defined as participants who consent to participate in the clinical study but are not subsequently assigned to study intervention. A minimal set of screen failure information is required to ensure transparent reporting of screen failure participants to meet the Consolidated Standards of Reporting Trials (CONSORT) publishing requirements and to respond to queries from regulatory authorities. Minimal information includes demography, screen failure details (eg, failed eligibility criteria), and any AEs, including any serious adverse events (SAEs) and any related concomitant medication, occurring during the Screening Period.

Individuals who do not meet the criteria for participation in this study (screen failure) due to a reason that is expected to resolve or has resolved may be rescreened based on discussion and agreement between the Investigator and the Medical Monitor. Rescreened participants are not required to re consent as long as they have signed the latest version of the ICF.

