4. STUDY DESIGN

4.1. Overall Design

This study will be conducted as an open-label, repeat-dose study to evaluate the effects of ALXN1840 on copper balance in participants with WD.

Treatment-experienced (which includes standard of care therapies or ALXN1840) and treatment-naïve participants are eligible for this study. Eligible patients will be classified into one of two cohorts:

- Cohort 1 (treatment experienced): Patients who have received WD therapy for > 28 days
- Cohort 2 (treatment naïve): Patients who have received WD therapy for ≤ 28 days

Following screening and enrollment, participants will check-in to the CRU on Day -8 for the Run-in Period. The purpose of the Run-in Period is to support diet equilibration (Day -7 through Day -5) and measure pretreatment copper and molybdenum balance (Day -4 through Day -1). Participants will remain on a copper/molybdenum-controlled diet throughout both the Inpatient Period 1 (Day -8 to Day 9) and Inpatient Period 2 (Day 23 to Day 40). While not in the CRU, participants will be encouraged to adhere to their usual copper-controlled diet.

Participants who are taking copper-chelating therapies (penicillamine or trientine) at the time of enrollment will be discontinued from their decoppering therapies starting on Day -4 to allow a baseline assessment of copper/molybdenum balance prior to ALXN1840 treatment. On Day 1, participants will be initiated on 15 mg/day of ALXN1840 for a treatment period of approximately 28 days followed by titration up to 30 mg/day on Day 29. Before titration to 30 mg/day, the SRC will review available safety data through Day 23 for each participant.

Participants will have intake and output collection periods from Day -4 through Day -1, from Day 1 through Day 8, and Day 25 through Day 39. The collection periods will support an assessment of both copper and molybdenum balance (as a measure of ALXN1840 ADME) at the 15 mg and 30 mg doses and will allow assessment of the effects of duration of treatment on copper elimination and copper balance.

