During the Outpatient Period, participants will be encouraged to remain on a copper-controlled diet; however, to avoid confounding, a diet equilibration period is included in each study period. Overall, collection periods are a minimum of 3 days and as long as 15 days (which will be subdivided for analyses). Collection periods of at least 3 days were used to help minimize the impact of day-to-day variability on measurements. In addition, the time period for analysis will take into consideration the average bowel transit of approximately 40 hours (male: 33 hours; female: 47 hours) (Camilleri, 1986; Metcalf, 1987). Because the periods are of different lengths, the study will calculate mean daily copper balance.

While the primary endpoint for the study is an assessment of net copper balance, measurement of a pretreatment copper baseline will be helpful to understand the magnitude of effect of ALXN1840. To assess the copper baseline during the Inpatient Run-in Period, participants will be discontinued from their chelator therapy for approximately 4 days prior to initiating ALXN1840. During this period, participants will be maintained on a copper-controlled diet to minimize risk to the participants. In the Phase 3 study ALXN1840-WD-301, participants discontinue their chelator approximately 48 hours prior to initiation of ALXN1840 without reported complications. Among participants who discontinue chelator due to intolerance or noncompliance, the time from chelator discontinuation to the onset or worsening of symptoms varies from as little as 1 or 2 weeks to as long as months or years (Scheinberg, 1987). To prevent confounding of the study results, participants must be off zinc therapy for a minimum of 21 days prior to Day 1 because zinc works through upregulation of metallothionein (MT) in enterocytes resulting in elevation of fecal copper excretion. Previously, reports in the literature suggest that it can take up to 3 weeks or longer for zinc treatment to have an efficacious effect on copper balance (Brewer, 1983), so a delayed time to reversal of this effect could also occur. However, the physiologic turnover of human gastrointestinal epithelial cells is 3 - 5 days (Darwich, 2014); therefore, the inhibitory effect of zinc on intestinal copper absorption is expected to be minimal 21 days after discontinuation of zinc.

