8. STUDY ASSESSMENTS AND PROCEDURES

- Study procedures and their timing are summarized in the SoA (Section 1.3). Protocol waivers or exemptions are not allowed.
- Immediate safety concerns should be discussed with Alexion immediately upon occurrence or awareness to determine if the participant should continue or discontinue study intervention.
- Adherence to the study design requirements, including those specified in the SoA, is essential and required for study conduct.
- All screening evaluations must be completed and reviewed to confirm that potential participants meet all eligibility criteria. The Investigator will maintain a screening log to record details of all participants screened and to confirm eligibility or record reasons for screening failure, as applicable.
- The following only applies to sites in the US.
 - In the US only, it is permissible for study visits for individual participants to occur at more than 1 site. Some sites may perform screening procedures only and not any of the remaining study procedures. These sites will be known as “screening sites”. The procedures performed at screening sites are defined in the Screening column (Study Days -42 to -9 and -21) of the SoA (Section 1.3). Following the completion of screening procedures at a screening site, eligible participants will be transferred to the CRU, where the remaining study procedures and visits will occur. Site-to-site transfer of the participant will be documented accordingly.

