9.3. Populations for Analyses

The population sets used for analysis are defined [Table 8](#).

Table 8: Populations for Analysis

Population	Description
Screened	All participants who sign the ICF.
Enrolled	All participants who sign the ICF, are eligible for the study, and are registered on Day -7 when participants are assigned a participant number.
Safety Analysis Set	All participants who receive at least 1 dose of ALXN1840 treatment.
Full Analysis Set	All participants who receive at least 1 dose of ALXN1840 treatment.
Per Protocol Set	All participants who received at least 1 dose of ALXN1840, had Baseline and all post Baseline values of copper intake (in food and drink) and copper output (in feces and urine), and were 100% compliant with study drug dosing. Participants with major protocol deviations that are likely to impact the primary endpoint analysis will be excluded from the Per Protocol (PP) Set. Major protocol deviations, and the PP Set, will be defined, documented, and agreed within Alexion prior to database lock.
Pharmacokinetic/Pharmacodynamic Analysis Set	All participants who have sufficient plasma samples to enable the calculation of PK parameters and provide PK/PD profiles.

Abbreviations: ICF = informed consent form; PD = pharmacodynamic; PK = pharmacokinetic.

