7.3.1. Study Duration, Treatment Compliance, and Exposure

Study duration will be summarized for all enrolled participants by cohort and overall. Study duration is defined as the time from first dose to the EOS or study discontinuation date (whichever occurs first) + 1.

Compliance during the Inpatient and Outpatient periods will be determined as the days taken / the days expected to be taken during active study treatment x 100. Treatment compliance will be summarized using descriptive statistics within cohort and overall. If a subject prematurely discontinues, his or her compliance will be based on the period up to the point of discontinuation from the study. Compliance will also be summarized using counts and percentages by compliance category (ie, $\geq 100\%$ compliance, 80 to $<100\%$ compliance, 60 to $<80\%$ compliance, etc.). A supporting listing will also be produced.

Exposure will be summarized for the Safety Set by cohort and overall. The duration (days) of exposure to treatment for each period will be calculated as date of last exposure to treatment – date of first dose + 1. The actual duration of treatment will be calculated as the exposure period – number of days on which treatment was temporarily stopped. The duration of exposure, average daily dose (mg), minimum daily dose (mg) and maximum daily dose (mg) for each period (as described in Section 7.2.1), and overall, as applicable will be summarized using descriptive statistics. Listings of exposure, drug interruptions and missed doses will also be presented.

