7.3.2.1. Overall Summary of Adverse Events

An overall summary of TEAEs will be presented, including number of events and number and percentage of participants experiencing AEs. Percentage will be calculated as $n/N*100$, where n is the number of participants with events and N is the number of participants in the Safety Set. The summary will include categories indicating how many events are TEAEs, treatment-emergent SAEs, and treatment-emergent non-SAEs. Within TEAEs, the following subcategories will also be summarized:

- Toxicity of TEAEs (Grade 1 through Grade 5)
- Related TEAEs (not related, related)
- TEAEs leading to withdrawal of study drug
- TEAEs leading to withdrawal from the study
- TEAEs leading to death

A summary of events (E) and number of participants with events (n, %) for pre-treatment emergent events (PTAEs) will also be included with its relevant subcategories.

A listing of all TEAEs by participant will be presented. Separate listings will be produced for SAEs, AEs leading to study drug withdrawal, AEs resulting in death, AEs leading to withdrawal from the study and PTAEs.

7.3.2.2. Adverse Events and Serious Adverse Events by System Organ Class and Preferred Term

The number of TEAEs and the number and percentage of participants with events will be presented by SOC and PT. Participants are counted once in each SOC and PT. Percentages will be based on the Safety Set. The SOCs will be listed in alphabetical order and PTs within each SOC will be listed by descending frequency. If needed, terms will also be ordered alphabetically.

Treatment-emergent SAEs, treatment-emergent non-SAEs, TEAEs leading to withdrawal of study drug, TEAEs leading to withdrawal from the study, TEAEs leading to death, and PTAEs will be summarized using the same approach.

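### Pre-treatment adverse events are tabulated only for dosed participants, so a washout event that prevents dosing enters no AE summary table

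*Protocol*

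**What the plan says.** **Washout.** Protocol 4.2 says that "participants must be off zinc therapy for a minimum of 21 days prior to Day 1", and the Schedule of Activities places the zinc stop at Day -21. Under Protocol 4.1, participants on penicillamine or trientine "will be discontinued from their decoppering therapies starting on Day -4".

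**Status.** Protocol 9.3 (Table 8) defines Enrolled as "All participants who sign the ICF, are eligible for the study, and are registered on Day -7 when participants are assigned a participant number". Protocol 5.4 states: "Screen failures are defined as participants who consent to participate in the clinical study but are not subsequently assigned to study intervention". The minimum data for screen failures include "any AEs, including any serious adverse events (SAEs) and any related concomitant medication, occurring during the Screening Period". Protocol 8 identifies the screening procedures by the "Screening column (Study Days -42 to -9 and -21") of the schedule.

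**Analysis sets.** SAP 6.5 limits the Safety Set to participants with at least one dose, and SAP 7.3 bases the safety analyses on it. For the overall AE summary, SAP 7.3.2.1 says "N is the number of participants in the Safety Set", and the same section includes PTAEs. SAP 7.3.2.2 tabulates PTAEs by system organ class and preferred term as it does treatment-emergent events, with Safety Set percentages. No AE table is planned on the Enrolled or Screened Set.

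**Listings.** SAP 7.1.1 plans listings of screen failures, of reasons for discontinuation, and of all enrolled participants with set membership and reason for exclusion. SAP 7.3.2.1 plans separate SAE and PTAE listings.

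**Study duration.** SAP 7.3.1 says "Study duration will be summarized for all enrolled participants by cohort and overall", but counts duration from first dose.

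**The concern.** Stopping established Wilson disease therapy is an exposure that the study imposes before any ALXN1840 is given. A PTAE by definition precedes the first dose. Requiring a later dose before the event can be tabulated therefore selects on a possible consequence of the event: those who got through the washout are counted, and anyone whose event kept them from being dosed is not.

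The schedule creates that route. Under the Schedule of Activities, safety laboratory samples are drawn on Day -1 and eligibility is checked again on Day 1. Protocol 5.2 excludes ALT above 2 × ULN and hemoglobin below the reference range. A participant whose values worsen off therapy could fail at that point.

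What is at stake is the summary of how well the washout was tolerated. The risk table in Protocol 2.3.1 does not list interruption of prior therapy. The reassurance in Protocol 4.2 cites a chelator interruption of about 48 hours in another study, against about 4 days here. The PTAE data are this study's own evidence on the matter, and SAP 4 says the interim analyses support regulatory submissions.

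**Working it through.** The plan gives no figure to reproduce. The check is a day count, a reading of the sets side by side, and an illustration.

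**1. Day counts (there is no Day 0).**
- Zinc: Days -21 to -1 = 21 days. Of these, Days -21 to -8 = 14 precede enrollment (13 of them, Days -21 to -9, lie in the screening column) and Days -7 to -1 = 7 follow it.
- Chelator: Days -4 to -1 = 4 days, all after enrollment and none in the screening column.
- Enrolled but not yet dosed: Days -7 to -1 = 7 days.

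**2. Where a washout event in a never-dosed participant would appear.**

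| Place | Population | Undosed participant included? |
|---|---|---|
| AE collection (Protocol 8.3.1) | From consent | Yes |
| Set-membership listing (SAP 7.1.1) | Enrolled | Yes, if enrolled |
| Screen-failure listing (SAP 7.1.1) | Screen failures | Yes, if so classed; content not specified |
| PTAE and SAE listings (SAP 7.3.2.1) | Not stated | Unclear; the general rule in SAP 7.3 could exclude them |
| PTAE summary tables (SAP 7.3.2.1, 7.3.2.2) | Safety Set | No |

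**3. Status between Day -7 and Day 1.** The study is single-arm and not randomised (Protocol 6.3), and nothing fixes when a participant is assigned to study intervention. If it is at registration, a later loss is enrolled and not treated. If it is at first dose, the same person also meets the wording of Protocol 5.4, and that section's minimum AE data, limited to the Screening Period, would miss the whole chelator washout. Collection would then rest on Protocol 8.3.1 alone.

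**4. Illustration.** Assume 10 dosed participants with no PTAE, and k further enrolled participants who each have a washout event and are never dosed. The Safety Set table shows 0/10 for every k. The Enrolled Set gives k/(10 + k):

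| k | Safety Set | Enrolled Set |
|---|---|---|
| 1 | 0/10 = 0% | 1/11 = 9.1% |
| 2 | 0/10 = 0% | 2/12 = 16.7% |
| 3 | 0/10 = 0% | 3/13 = 23.1% |

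Exact (Clopper-Pearson) 95% intervals are 0 to 31% for 0/10 (upper limit 1 − 0.025^(1/10) = 0.308), 0.2 to 41% for 1/11 and 2 to 48% for 2/12. They overlap widely. What changes is whether an event is seen at all, more than any estimate of a rate.

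**5. How likely k ≥ 1 is.** The documents give no rate. If each of 11 participants independently has probability p of such a loss, the chance of at least one is 1 − (1 − p)^11: 0.105 for p = 0.01, 0.431 for p = 0.05 and 0.686 for p = 0.10. All three values of p are assumptions.

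**The case against.** **The event is not lost.** AEs and SAEs are collected from consent, and SAEs go to the sponsor within 24 hours (Protocol 8.3.1). SAP 7.1.1 and 7.3.2.1 plan the listings above. With about 10 participants, listings are a main display, and SAP 7 allows listings alone when numbers are small. This stands, and it confines the point to the summary tables and to the unstated population of the AE listings. A reader might infer that washout harm vanishes from the study's reporting; the documents do not support that.

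**Enrolled participants do not become screen failures.** A reader might infer that an enrolled, never-dosed participant is reclassified as one. Protocol 5.4 speaks of assignment, not dosing. It also links screen failure to not meeting the participation criteria, whereas enrolled participants have been found eligible. SAP 7.1.1 places screening exclusions before enrollment. The text is ambiguous and, if anything, leans the other way. Overlapping disposition counts are therefore possible, not established.

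**Washout risk is not an objective.** The safety objective concerns repeated ALXN1840 dosing, and a PTAE table on treated participants is a legitimate pre-treatment history. That is fair. It also means the documents do not support saying that the trial would report the washout as safer than it was. The limited table still cannot describe tolerability of the washout, and nothing in the SAP warns of this.

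**A preventing event may be unlikely.** Protocol 4.2 puts symptom onset after stopping a chelator at 1 to 2 weeks at the earliest, against about 4 days here. This weakens the chelator half. For zinc, stopped for at least 21 days, the documents give no such timing.

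**The denominators are not washout rates.** Treatment-naïve participants are eligible and may have stopped nothing, so 1/11 is not a risk among those who stopped therapy. This stands, and the fix allows for it.

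**Conclusion.** The point holds in a limited form. As written, an AE during the mandated washout that prevents dosing enters no AE summary table, and whether it enters the PTAE and SAE listings is not stated. The cause is the choice of analysis set; collection is adequate.

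The size is illustrative only. The contrast of 0/10 with 1/11 assumes one enrolled participant lost to a washout event and no PTAE among 10 dosed participants. Nothing in the documents shows that such a loss has happened or is likely.

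Two wording defects go with it. The moment of assignment in Protocol 5.4 is undefined. Study duration in SAP 7.3.1 cannot be computed for an enrolled participant with no first dose; the value would be missing and no result biased.

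The primary copper balance analysis, on the Full Analysis Set, and treatment-emergent AE reporting are unaffected. This is a cheap improvement worth making before the tables are produced.

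**What to change.** 1. **SAP 7.3, 7.3.2.1 and 7.3.2.2.** Summarise and list PTAEs and pre-treatment SAEs on the Enrolled Set. Add a separate line for participants who stopped zinc for the study but were not enrolled. Show how many in each group had stopped prior therapy, and give the reason for not being dosed. State that every AE in a never-dosed participant counts as pre-treatment, because SAP 9.2.1 classifies events by a first-dose date that such a participant lacks. Keep treatment-emergent AEs on the Safety Set.
2. **Protocol 5.4.** State when assignment to study intervention occurs, so that losses between Day -7 and Day 1 are reported as enrolled, not treated.
3. **SAP 7.3.1.** Either summarise study duration on the Safety Set or start it at enrollment.

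The cost is wording in both documents. The Enrolled Set is already defined and AEs are already collected from consent, so no new data or procedures are needed. The downside is that PTAE and treatment-emergent tables will have different denominators, which must be labelled.
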